Group and of recruiting, retaining and collecting outcome data with the target population, to pave the way for a definitive trial of this intervention. The results of this study will be used to inform a larger definitive trial of this intervention in CSC. In the Table below we specify the research questions and how we aim to address them.

Generic questions	Specific questions	Indicators
1. Is it possible to recruit and retain participants to an evaluation of the Fathers Group and collect quality outcome data?	Q1. Is it feasible to recruit participants?	Recruitment pathways. Recruitment rate (to intervention and to study). Demographic characteristics of the sample. Scoping survey with other local authorities.
	Q2. Is it possible to retain participants throughout the evaluation?	Number of referrals, proportion consenting and completing the intervention ($\geq 70\%$ of sessions), proportion consenting to study and completing post-test.
	Q3. Is it possible to collect quality outcome data?	Participant retention rates at baseline, post-test and follow-up.
	Q4. Is a third assessment point at 3-month follow-up feasible?	Document drop-out reasons. Data completion rates. Qualitative findings from focus-group and 1:1 interviews with fathers to understand data collection experience.
	Q5. What strategies are effective for data collection?	Data collection approach – document comparative success of different strategies and modify accordingly.
2. Are the outcomes quantifiable?	Q1. Are the outcome measures acceptable and able to detect change?	Changes, specifically escalation and de-escalation, in CSC involvement, parental and caring responsibility, level of contact, and domestic violence reports.
	Q2. What is the distribution of the outcome measures?	Pre- and post-treatment outcome data using standardised measures: 1) father's reported child abuse potential (CAPI), 2) father's mental health and wellbeing (CORE-10, PSF-sf),
	Q3. What are the recommended outcome measures (and effect size estimates) and	3) father's parenting and family dynamics (SCORE-15, PSS, APQ, b-PSES),

procedures for a future trial?

4) children’s socio-emotional and behavioural difficulties (SDQ- parent, partner, and older-child report),

5) partner’s reported intimate partner violence occurrence (WAST) and SCORE-15;

6) stages of change (from URICA).

Qualitative focus groups and 1:1 interviews with fathers (to gather views regarding study processes and instruments)

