Q4. What is the estimated sample size needed for an RCT?

Effect size estimates to do power analysis.

3. Is the programme acceptable to fathers and the network of professionals around them, and is it generalisable?

Q1. How did fathers experience the intervention?

Rates of completion of intervention.
Qualitative focus-group and 1:1 interviews with fathers.

Q2. What are professionals’ views about the intervention?

1:1 interviews with professionals in the local authority.
Survey mailout to other local authorities.

Q3. What are the barriers to and facilitators of the intervention?

Drop-out reasons.
Qualitative focus-group and 1:1 interviews with fathers and professionals in the local authority.
Survey mailout to other local authorities.

Q4. Will the intervention fill a gap in local authorities’ service provision?

Survey mailout to other local authorities.

Q5. Is the programme generalisable to other facilitators and other sites?

Detailed characterisation of the programme and the training requirements of facilitators to allow scaling up.

4. Is a cost evaluation feasible and what are the

Q1. What is the cost of delivering the Group compared to alternative interventions?

Estimated cost of delivering each Group and scoping of the cost of comparable interventions.

recommended procedures to calculate it?

Q2. Can quality data be collected for the cost evaluation?

Scoping of other services offered to the fathers, referrals to services and timings, and uptake of these services (i.e. “care as usual”).

Feasibility of collecting service use data from fathers, families and professionals, and access to care notes.

5. What is the most suitable design for a future large scale trial?

Q1. Is it feasible to randomise participants within one local authority?

Feasibility of recruiting a sufficient number of fathers to each Group and the timing of these referrals (+implications for treatment arm allocation)– from referral pathways and recruitment rates (to intervention and to study).

Acceptability of randomisation processes – from focus-groups and 1:1 interviews with fathers, interviews with local authority stakeholders and survey with other local authorities.

Q2. What are professionals’ views about the feasibility of a future trial?

1:1 interviews with professionals in the local authority.

Survey mailout to other local authorities.

Q3. What characterises care-as-usual?

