Services available to fathers in this site and other local authorities – from interviews, survey, and literature review.

Note. CAPI= Child Abuse Potential Inventory, CORE-10= Clinical Outcomes in Routine Evaluation, PSS= Parental Stress Scale, SCORE-15= Describe your family, APQ= The Alabama Parenting Questionnaire, b-PSES= The brief-Parental Self Efficacy Scale, QCCS= Quality of Co-parental Communication Scale, CoPRS= Co-parenting Relationship Scale, SDQ= Strengths and Difficulties Questionnaire, WAST= Women Abuse Screening Potential, URICA= University of Rhode Island Change Assessment Scale.

Methods

Sample and recruitment

The study aims to recruit 48 male carers who take part in one of three cohorts of the Group starting Autumn 2023, January 2024, and Spring 2024, totalling 16 parents per Group. The intervention facilitator will share information about the upcoming Groups among referring social workers. They will be able to refer fathers between August 2023 and March 2024, and fathers will then be assigned to the next upcoming Group. Referrals will be received on a rolling basis from social workers throughout this period. Social workers will be contacted by the lead facilitator – this could

be either in person or over the phone or email, with the support of a written leaflet to share information about the study. Fathers of a 4–12-year-old with a social worker, who accepted taking part in the Group intervention during one of the three cohorts, are eligible to the study.

Once fathers agree to take part in the Group, the Group facilitator will ask for their verbal consent to pass their contact details to the research team. The Group facilitator will also give potential participants a leaflet containing summary information about the study. A member of the research team will then contact fathers to explain and invite them to the study. Consenting fathers will be asked to read a Participant Information Sheet (PIS), complete an Informed Consent Form (ICF) online and complete the baseline assessment. Fathers' consent will include their agreement to being contacted by the research team after completion of the Group. At the end of the 10-week programme the research team will contact participants again to ask for their participation in the post-treatment assessments. Fathers' agreement or refusal to take part in the study will not affect their involvement in the intervention programme.

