To establish the feasibility and acceptability of baseline and outcome assessments, we will calculate proportions and 95% CIs of: (i) cases completing baseline assessments, from those recruited to study; (ii) cases completing post-treatment assessments, from those recruited to study; (iii) cases completing follow-up assessment, from the subset of participants invited to a 3rd time-point. Data completeness will be reported based on proportion of cases with complete data and percentage of data completeness for key outcome measures, as well as patterns in data missingness. Acceptability of the outcome measures will be further examined in the qualitative interviews about participants' experience.

To test the feasibility of recruiting/consenting fathers' relatives to the study, proportions and 95% CIs will be calculated for: (i) fathers with a resident partner/ child consenting for them to being invited to study; (ii) proportion of eligible partners/children consenting to study; (iii) proportion of consenting partners/children completing baseline and post-treatment outcome measures.

The relative success of different modes of data completion and the required support for completion will be documented.

Recruitment pathways and demographic characteristics of participants will also be summarised to document the recruitment process.

RQ2. Are the outcomes quantifiable?

In addition to consideration of the completion rates described above, the ability of measures to detect change, ceiling/floor effects in questionnaires, and participant feedback from qualitative interviews, will be synthesised to preliminarily identify the most appropriate primary outcome. We will also explore the evidence of the promise of the intervention to affect behaviour and symptom change by presenting pre/post-treatment differences (with confidence intervals).

We will further obtain the distribution and initial estimates of variance of key outcome measures for power analyses to estimate the sample size needed for a future trial.

RQ3. Is the programme acceptable to fathers and the network of professionals around them, and is it generalisable?

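### The Protocol names effect sizes from a single-arm study as the input for sizing the future RCT in one place and only variance in another, and gives no other source for the target difference

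*Protocol*

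**What the plan says.** The Protocol describes the basis for the future trial's sample size in two places.

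- **Research questions table, generic question 2.** Q3 begins "What are the recommended outcome measures (and effect size estimates) and" and goes on to the procedures for a later trial, so an effect size is an intended product of the study. Q4 asks for the RCT sample size, and its only indicator is "Effect size estimates to do power analysis".
- **Analysis, RQ2.** The stated power input is different: the distribution of the measures and "initial estimates of variance of key outcome measures for power analyses to estimate the sample size needed for a future trial". Pre/post differences with confidence intervals appear in the same section, but to explore whether the Group looks promising.

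On design, Sample and recruitment states: "The study aims to recruit 48 male carers who take part in one of three cohorts of the Group". There is no comparison arm. The Background notes this limitation for the earlier evaluation of 36 fathers, but the caveat is not repeated where the power analysis is described.

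On the primary outcome, RQ2 lists completion rates, "the ability of measures to detect change", floor and ceiling effects, and qualitative feedback, which "will be synthesised to preliminarily identify the most appropriate primary outcome".

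**The concern.** A sample size calculation for a two-arm trial with a continuous outcome needs a variance and a target difference. The analysis section supplies the first. The only candidate the Protocol names for the second is the effect size in the research questions table, and in this design that can only be a within-group change.

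Such a change is not a treatment effect. Fathers enter while their child has a social worker, which is a time of concern, so some movement towards the average is plausible without the Group. Other services and the passage of time contribute too. A controlled trial removes these components from the comparison; a power calculation fed with the raw change leaves them in.

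The choice of outcome could compound this. If a measure is favoured partly because it moved, and the same movement is then used for sizing, the same chance variation is counted twice.

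The recommended outcome, the effect size and the RCT sample size are explicit study questions. An RCT sized too optimistically could fail to show a real benefit of the Group.

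**Working it through.** **No figure to reproduce.** The Protocol states no RCT sample size, effect size, SD, alpha, power or pre/post correlation. What follows is illustrative, with the assumptions named.

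**Inputs.** From the Protocol: 48 fathers (3 cohorts of 16), and about 70% previously completing the Group (Risks). Taking Group completion as a stand-in for post-test completion, 48 × 0.70 = 33.6, or about 34 pairs. Assumed: two-sided alpha 0.05, 80% power, 1:1 allocation, SD 1, pre/post correlation r of 0.5 to 0.7.

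**1. Precision of a pre/post effect size.** SE = √[2(1−r)/n + d²/(2(n−1))]. For an observed d of 0.3:

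- n = 48, r = 0.5: SE = √(1/48 + 0.09/94) = 0.148; 95% CI 0.01 to 0.59.
- n = 48, r = 0.7: SE = 0.116; 95% CI 0.07 to 0.53.
- n = 34, r = 0.5: SE = √(1/34 + 0.09/66) = 0.175; 95% CI −0.04 to 0.64.

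The estimate is too imprecise to size a trial even before any bias.

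**2. Effect of having no control.** n per arm = 2(1.96 + 0.842)²/d² = 15.70/d². Power at a planned n is Φ(d√(n/2) − 1.96). Suppose the study observes 0.5 SD and the RCT is planned on it: 15.70/0.25 = 62.8, so 63 per arm (about 64 with the t distribution). The controlled effect is 0.5 minus whatever untreated fathers would have changed.

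| Untreated change (SD) | Controlled effect (SD) | Needed per arm | Needed ÷ 63 | Power with 63 per arm |
|---|---|---|---|---|
| 0 | 0.5 | 63 | 1.0 | 80% |
| 0.1 | 0.4 | 99 | 1.6 | 61% |
| 0.2 | 0.3 | 175 | 2.8 | 39% |
| 0.3 | 0.2 | 393 | 6.2 | 20% |

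For the third row: 15.70/0.09 = 174.4, so 175; and 0.3 × √31.5 − 1.96 = −0.28, so Φ = 0.39. Baseline adjustment in the RCT multiplies every n by 1 − r² and so leaves the ratios essentially unchanged. At r = 0.5, the 63 and 175 become 48 and 132.

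**3. Effect of selection, if it were applied strictly.** Data collection lists eight father-reported scales: CAPI, CORE-10, PSS, SCORE-15, APQ, b-PSES, SDQ and the URICA items. Suppose all truly change by 0.3 SD, none of it untreated change, and the largest observed change is used for sizing. Over n of 34 to 48, r of 0.5 to 0.7 and between-scale correlation of 0 to 0.5, the expected largest change in 20,000 simulated studies is 0.41 to 0.55 SD. That plans 93 down to 53 per arm where 175 are needed, for true power of 53% down to 34%.

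**4. Using variance alone, as the analysis section says.** The 95% limits for the SD are 0.83 to 1.25 times the estimate at n = 48 and 0.81 to 1.32 times at n = 34. For a fixed raw target difference, the required N scales with the square: 0.69 to 1.57, or 0.65 to 1.73, times the planned N. This is imprecise, but the lack of a control does not inflate it. A one-sided 80% upper limit would multiply the SD by 1.10 (n = 48) or 1.13 (n = 34).

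**The case against.** The strongest reply is that the indicator is a short cell in a summary table, while the detailed analysis section uses the study for variance, which is the accepted purpose of a feasibility study, and gives pre/post differences a separate, exploratory role. A reader might infer from the table that the RCT **will** be sized on the uncontrolled change. The Protocol does not commit to that: nowhere does it say that the observed change will be the target difference. This stands, so the defect is an inconsistency with a gap. It does not clear the plan, because variance alone cannot size a trial and no other target difference is named.

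A reader might also infer that the primary outcome goes to whichever measure moves most. No such rule is stated. Responsiveness is an ordinary measurement criterion, it is one of several here, and the choice is described as preliminary. The URICA items are also an unlikely primary outcome. Step 3 is therefore a worst case.

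Nor can it be said that the RCT will be far too small. There is no planned N to judge, and the shortfall depends on an untreated change that nobody has measured. It could be nil, and if untreated fathers worsened the bias would run the other way.

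The figure of 34 pairs is also only a proxy, since post-treatment assessment is not restricted to fathers who complete the Group. Finally, the target difference may be set in a document not shown here or in the RCT's own protocol. Even so, the table already states an input, and it is an unsuitable one.

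**Conclusion.** The point holds as an inconsistency that should be fixed. The research questions table points the RCT power analysis at effect sizes that this single-arm design can supply only as uncontrolled change. The RQ2 analysis section points it at variance, and neither names a sound source for the target difference.

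If the pre/post change were used, the RCT would probably be too small. The shortfall runs from none, when untreated fathers do not change, to 63 per arm against 175 needed (39% power) when 0.2 SD of an observed 0.5 SD is untreated change, and more beyond that. These sizes rest on the assumed alpha, power and observed change. Selecting on observed change could add to the bias, but only if that same change is then used for sizing. The conduct of the present study and its participants are not affected.

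**What to change.** Bring the Q3 and Q4 entries of the research questions table into line with Analysis, RQ2. Replace the Q4 indicator with wording such as:

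> The RCT sample size will use this study's SD (with allowance for its imprecision, for example an upper confidence limit), pre/post correlation and retention, with a target difference from a justified minimally important difference or controlled evidence, not from this study's pre/post change.

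The choice of confidence limit for the SD is a convention; a one-sided 80% limit is one option among several.

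In RQ2, report the pre/post change for every measure descriptively, with its confidence interval. State that the size of observed change will not decide the primary outcome, which will rest on completeness, floor and ceiling effects, acceptability and relevance.

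The cost is a few sentences and no new data, plus the work of justifying an important difference for the candidate measures. The projected RCT may turn out larger.

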Some fathers may have low literacy levels. This will be mitigated as the study can be verbally explained by the researchers when seeking the fathers' consent. In all cases, the research team will make themselves available to clarify any questions and offer different formats (online, telephone, face to face) to support participants' decisions about taking part. The research team and the Participant Information Sheet (PIS) will also make it very clear that taking part in the research is voluntary, that participants have the right to withdraw at any stage and that the research team is independent from social services. If participants require additional support, they will be given the option of completing the Informed Consent Form (ICF) with a researcher via Microsoft Teams or in person at the Southwark site.

Fathers who live with a partner (regardless of biological and parental responsibility for his children), will be asked in their ICF if they agree to the research team inviting their partner to the study. If the father agrees with this contact, and provides their partner's contact details (or the partner contacts the research team directly), the research team will contact the partner to invite them to complete a survey relating to family dynamics, whether their partner is violent and their child's wellbeing. If the partner wishes to take part, they will be asked to read a PIS and sign the online ICF before completing the questionnaires. Some partners may have low literacy levels. This will be mitigated as the study can be verbally explained by the researchers when seeking the partners' consent. Partners' willingness to take part in the study will not affect fathers' ability to participate.

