Survey for partners	
Treatment outcome measures assessing partners' reported intimate partner violence occurrence and family dynamics, as well as the child's socio-emotional and behavioural difficulties:
 
 • SCORE-15 Index of Family Functioning and Change; • Women Abuse Screening Tool (WAST); • Child's Strengths and Difficulties Questionnaire (SDQ). 
Data will be collected online via MS Forms and RedCAP. Participants will be sent a link to complete the survey. It is expected the survey will take approximately 15 minutes to complete.
 
Partners will receive a £5 voucher for each set of questionnaires they complete.
	Estimated approx. 30	Baseline and post-treatment.
			
The survey will be shared the week before the first and after the last Group session.

Survey for older children	
Children aged 11–12 will complete a child-report SDQ about their wellbeing online. If the children cannot complete the questionnaire independently they will have the option to complete it with a research assistant online or be given a physical copy of the questionnaire either via post or via their father when he attends the Group. Carers with parental responsibility will be sent a link to share the survey with their child. It is expected the survey will take 10 minutes to complete.
	Estimated max. 48	Baseline and post-treatment.
Sub-study: survey for fathers and partners	
For one Group cohort only, the same questionnaire measures for father, child and partner will be collected at a third timepoint.
 
Data will be collected online via MS Forms and RedCAP. Participants will be sent a link to complete the survey. It is expected the survey will take approximately 60, 15, and 10 minutes for fathers, partners and children to complete, respectively.
	16 fathers; max. 16 carers; estimated max. 16 children	
3-month follow-up.
 
The survey will be shared 12 weeks after the last Group session.

Focus group with fathers	
Focus groups will be conducted with the fathers, after each of the three cohorts completes the programme. Focus groups will be led by the research team either on site after the last session of the programme, or online. They are expected to take 1 hour, and will be recorded
	Max. 48, across 3 focus groups	Post-treatment.

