Currently, the intervention is delivered by one practitioner (with support from additional facilitator(s)) and there is heavy reliance on him to recruit and facilitate the Group. This creates a risk for the sustainability of the programme if this practitioner became unavailable to deliver the sessions. The additional risk that this creates for a future scaling up of the intervention will be further investigated and mitigated in this study, by collecting more detailed information about the programme and the training requirements of additional practitioners for a future large-scale trial. Medium risk.

Lack of definition of the intervention

As a non-manualised and not previously published intervention, there is a risk that the programme will fail to be systematically replicated in other sites. To mitigate this risk, an intervention protocol is being developed by the delivery partner, and the research team will collect detailed information about the delivery of the sessions to inform fidelity checks in a future trial. **Low risk.**

Data collection from the child and partner

There is a possibility that partners and children decline taking part in the research, particularly if their relationship with the fathers are strained. To encourage partners' participation, partners will receive vouchers for their time

completing each set of questionnaires. In addition, limited outcome measures will be collected from the partner and child, to decrease participant burden. Again, a flexible and compassionate approach to data collection will be used to facilitate trust and accommodate the needs of participants. **Low risk.**

Research team becoming aware of elevated distress from parents or children

If parents or children are experiencing elevated distress (e.g., CORE-10 or SDQ symptoms in the clinical range), the research team will write a summary report to the referrer so that appropriate referrals or support can be put in place via the social worker.

Researchers will not be able to check the questionnaire responses immediately after completion. When participants' responses are checked and they indicate elevated distress, the researchers will also contact the participants via email or phone to remind them of the available sources of support, including how to access immediate support if needed. If relevant, safeguarding procedures will be followed. **Medium/Low risk.**

Safeguarding concerns

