The Groups and the evaluation study will be conducted in the CSC setting, where participants will be referred by the social workers themselves. Therefore, participating fathers and their families will be known to the social workers and already be engaged with CSC when invited to the study. Social workers that will become involved in the study have existing training in safeguarding and risk management as part of their job. Moreover, the intervention is being delivered by practitioners who are experienced working with this population and are embedded in the local authority's Family Early Help Parenting Service. As part of this research project, we have established safeguarding procedures, including identified safeguarding leads in each of the partners – which will be followed whenever necessary. **Medium risk.**

Safeguarding risks to the research assistants when conducting in-person assessments will be mitigated by doing these assessments at the same venue as the Group or another appropriate venue of the local authority, within working hours; home visits will not be offered. **Low risk.**

Partners being unable to complete questionnaires with confidentiality and safety, and/or giving rise to safeguarding concerns

There is a risk that partners' responses to the questionnaires might not be honest, if they do not feel safe enough to do so. This risk is inherent to this type of study but mitigated by the option that is given to participants to choose their preferred method of completion.

Safeguarding concerns may still arise (e.g., from scores on IPV questionnaire), and if they do they will be dealt with by following the procedures agreed between the project partners which includes contacting the relevant safeguarding leads. In addition, partners' PIS contains contact details to domestic violence support services. **Medium risk.**

Compliance

Registration

This study will be registered with the Open Science Framework (OSF).

Ethics

Ethical approval will be obtained from UCL Ethical Review Board before recruitment commences in September 2023.

Consent

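### Partner-reported violence (WAST) is collected only where the father permits it, and choice of completion method neither corrects that selection nor protects the contact channel

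*Protocol*

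**What the plan says.** Under Sample and recruitment, fathers who live with a partner "will be asked in their ICF if they agree to the research team inviting their partner to the study". The team then contacts the partner "If the father agrees with this contact, and provides their partner's contact details". A bracketed alternative is added: "or the partner contacts the research team directly". The partner survey covers family dynamics, "whether their partner is violent and their child's wellbeing".

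The data collection table (Survey for partners) lists the WAST with SCORE-15 and the SDQ at baseline and post-treatment, for about 30 partners. On mode it says: "Participants will be sent a link to complete the survey. It is expected the survey will take approximately 15 minutes to complete". The father row adds in-person completion with a researcher. The child row adds completion with a research assistant or on paper.

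The closing part of the family recruitment text in Sample and recruitment says the team will discuss preferred completion with every participant and offer telephone, video and in-person support. The Risks entry on partners' confidentiality and safety accepts that answers may not be honest where a partner feels unsafe. It calls this inherent to such studies but "mitigated by the option that is given to participants to choose their preferred method of completion". The same entry adds agreed safeguarding procedures and domestic violence support contacts in the partner information sheet.

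Under Analysis, RQ1 reports the proportion of fathers who agree to the invitation, with a 95% CI. RQ2 weighs completion, floor and ceiling effects and ability to detect change to identify a primary outcome. Domestic abuse records are collected separately as administrative data.

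**The concern.** The person whose behaviour is measured decides whether the measurement is attempted and normally supplies the telephone number or email address through which it is made. Two effects can follow. Fathers in violent relationships may refuse more often, so those partners are never invited. Partners who are invited may hold back if the father can see the channel. Either would lower the violence reported on the WAST.

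The stated mitigation addresses how a partner completes the survey. It does not address who was invited or whose device receives the link, and no section requires a check for a safe contact route or completion in private.

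The study is meant to judge which measures suit a definitive trial. A WAST distribution bunched at low scores could reflect selection and guarded answers, yet be taken as a floor effect or as little violence. A later trial that copied the same recruitment route would inherit the problem.

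**Working it through.** The protocol gives no violence, permission or disclosure rate, so there is no planned figure to reproduce. The check is first a comparison of sections, then an illustration on assumed values.

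**Order of events**

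1. The father agrees, in his own consent form (Sample and recruitment).
2. He supplies the details, or the partner contacts the team. As worded, the bracketed alternative replaces only the supply of details, not his agreement. How a partner would hear of the study independently is not stated.
3. The partner is contacted, reads the information sheet and signs the online consent form.
4. The partner receives a link (data collection table) or chooses another mode (Sample and recruitment; Risks).

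Choice of mode enters at step 4. It cannot change who passes steps 1 and 2, and it does not specify the channel used at step 3. The safeguarding procedures respond once a concern has arisen, and the support contacts reach only partners who have been approached.

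**Table against text**

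The partner row names a link and nothing else. The general statement in Sample and recruitment and the Risks entry both promise a choice. These need reconciling.

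**Illustration (all inputs assumed)**

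Let p be the true share of resident partners in violent relationships, a1 and a0 the permission rates of violent and other fathers, and s the probability that an affected partner discloses. The partner's own consent is taken as equal in both groups.

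Observed share = s × p·a1 / (p·a1 + (1 − p)·a0)

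With p = 0.30 and a0 = 0.80:

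| a1 | share among partners reached | s = 1 | s = 0.6 |
|---|---|---|---|
| 0.80 | 0.24 / (0.24 + 0.56) | 30.0% | 18.0% |
| 0.60 | 0.18 / (0.18 + 0.56) | 24.3% | 14.6% |
| 0.40 | 0.12 / (0.12 + 0.56) | 17.6% | 10.6% |

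At a1 = 0.40 and s = 0.6, a true 20% becomes 0.6 × 0.08/0.72 = 6.7%, and a true 40% becomes 0.6 × 0.16/0.64 = 15.0%. If a1 = a0 and s = 1 there is no bias.

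**Could the study detect such a shift?**

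With 30 partners, 9/30 (30%) has a 95% Wilson interval of 17% to 48%, and 5/30 (17%) has 7% to 34%. The intervals overlap widely, so the WAST data alone could not reliably show it.

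**The case against.** The strongest reply is that the protocol sees the risk, rates it medium and responds with mode choice, safeguarding leads and support contacts. It also lets participants skip sensitive items, reports how many fathers agree to the invitation, and holds domestic abuse records that do not depend on the partner. Estimating the prevalence of violence is not an objective, and the choice of primary outcome under RQ2 is only preliminary. The safeguarding procedures and the partner information sheet are not shown and may already cover safe contact.

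Much of this stands, and it rules out several stronger conclusions that a reader might draw:

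- *Partners have no alternative to the online link.* Not supported: the choice is promised to every participant and repeated in the partner risk entry. The table row is inconsistent with that; the option is not absent. Nor does the row say by what channel the link is sent.
- *In-person sessions default to the Group venue.* Not supported: Risks and Ethics both also allow another local authority venue.
- *Follow-up contact will reveal a disclosure of violence.* The contact in question, where "the researchers will also contact the participants via email or phone to remind them of the available sources of support", is triggered by elevated distress, with CORE-10 and SDQ scores as examples. Partners do not complete the CORE-10, and their SDQ concerns the child. Concerns from the violence questionnaire go through safeguarding leads.
- *Violence will be under-detected.* This needs permission or disclosure to depend on violence. That is plausible but not established. The planned figure of about 30 is a survey sample size and cannot be read as a permission rate.

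What the reply does not meet is the order of events. None of the safeguards stated in the protocol recovers partners whom the father declines to have invited or requires a private channel before the WAST is sent. Counting permissions shows how large the gate is, not whether those behind it differ.

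**Conclusion.** The point holds as a design weakness of moderate weight. WAST data are gated by the father, and the mitigation offered against dishonest answers acts after that gate and leaves the contact channel unprotected. The partner row also omits a mode choice promised elsewhere. The data may under-represent violent relationships, and low scores under RQ2 would have more than one explanation.

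The direction is likely downward; the size cannot be stated. The illustrated range for a true 30%, from no bias to about a third of the true value (10.6/30.0 = 0.35), rests wholly on assumed permission and disclosure rates. There is no bias if fathers' permission does not depend on violence and affected partners disclose fully.

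**What to change.** 1. Before any WAST link is sent, have a researcher ask the partner directly for a private contact route and preferred mode. Use only that route for links, reminders and follow-up. List telephone, videocall and in-person completion in the partner row of the data collection table, so that it agrees with Sample and recruitment and with Risks.
2. Add one item after the WAST, completed in private (yes/no), and report WAST results overall and by that item. A partner who is overlooked may also answer this item guardedly, so it is an aid to interpretation, not proof of privacy.
3. Tabulate the administrative domestic abuse records by whether the father permitted partner contact, among participating fathers with a resident partner. This assumes the pseudonymised records can be matched to the permission response. With so few fathers it can only be descriptive. State in the report that WAST results apply only to partners of fathers who permitted contact.

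The cost is a slightly longer partner contact (a direct conversation where consent would otherwise be wholly online), one survey item, one cross-tabulation of data already planned, and possibly a few lost partners. First contact may still use details the father supplied, and his veto stays in place, so these steps describe the selection and make later contact more private without removing the gate.
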